2.4 Subgroup analyses

None identified to date.

2.5 Patient demographics and other baseline characteristics

Unless noted otherwise, summaries and listings described in this section will be based on the FAS.

2.5.1 Basic demographic and background data

Demographic data including age, age categories (<65, ≥ 65 years), sex, race, ethnicity, height, weight, LVEF, and ECOG performance status at baseline will be listed and summarized.

2.5.2 Medical History

Medical history and current medical conditions will be coded using the latest Medical Dictionary for Regulatory Activities (MedDRA) terminology available at the time of reporting. Medical history and current (ongoing) medical conditions, including cancer-related conditions and symptoms will be available as listing.

2.5.3 **Prior antineoplastic therapy**

The number (%) of patients who received prior anti-neoplastic medications will be summarized and listed.

The summary of prior anti-neoplastic medications will include the total number of regimens (note: there can be more than one medication per regimen), therapy type at last medication, setting at last medication, best response at last medication (defined to be the best response during the last treatment regimens recorded), time (in months) from (end of) last medication to Progression,. The last medication is defined based on the last end date of all prior regimen components. Prior antineoplastic medications will also be summarized by Anatomical Therapeutic Chemical (ATC) class, and preferred term.

All Prior anti-neoplastic therapies (medications, surgery and radiotherapy) will be available at a patient level (listing).

2.5.4 Diagnosis and extent of cancer

The summary and listing of diagnosis and extent of cancer (disease history) will include primary site of cancer, details of tumor histology/cytology, histological grade, stage at initial diagnosis, stage at time of study entry time (in months) from initial diagnosis of primary site to start of study treatment, time (in months) since most recent recurrence/relapse or progression to start of

Novartis	Confidential	Page 11
SAP	13-May-2019 (11:03)	CLTT462X2101

study treatment, time (in months) from initial diagnosis of primary site to first recurrence/relapse or progression, current stage of cancer, current extent of disease (metastatic sites), and type of lesions (target and non-target lesions) at baseline.

2.6 Patient disposition

The FAS will be used for the patient disposition summary tables and listings. The following will be tabulated:

- Number (%) of patients who are still on-treatment,
- Number (%) of patients who discontinued treatment,
- Primary reasons for study treatment discontinuation,
- Number (%) of patients who are still on study,
- Number (%) of patients who discontinued from study,
- Primary reasons for study discontinuation.

2.7 **Protocol deviations**

The FAS will be used for the protocol deviation listing. The full list of protocol deviations is documented in the Study Specification Document (SSD).

2.8 Treatments (study treatment, concomitant therapies, compliance)

Unless otherwise noted, the safety set will be used for all summaries and listings described in this section.

2.8.1 Study treatment

Last date of exposure to LTT462 is the last date of study treatment.

Study treatment will be summarized in terms of duration of exposure to study treatment, cumulative/average daily study drug dose, study drug intensity (DI).

- Duration of exposure (days): last date of exposure to study treatment first date of study treatment + 1 (periods of interruption are not excluded)
- Cumulative dose (mg): sum of all total daily doses of study drug taken by a patient
- Cumulative planned dose (*mg*): sum of all doses of study drug that was intended to have been taken during the treated period by a patient
- DI (mg/day): cumulative dose (mg)/number of doses scheduled per protocol during treatment period
- Relative DI: Cumulative dose (mg)/Cumulative planned dose (mg)

The duration of exposure to study treatment will also be summarized following the categories: <4, <=4, <=8, <=12, <=16, <=24 weeks.

Relative RDI will also be summarized following the categories: $<0.5, 0.5-<0.75, 0.75-<0.9, 0.9-<1.1, \ge 1.1$ for each study drug.

A listing of patient's dose administration records will be presented.

Novartis	Confidential	Page 12
SAP	13-May-2019 (11:03)	CLTT462X2101

2.8.2 Concomitant therapies

Concomitant therapies are defined as any medications (excluding study treatment, prior antineoplastic treatments) and significant non-drug therapies (including physical therapy and blood transfusions) administered in the study and are recorded in the Concomitant Medications/significant non-drug therapies eCRF. These therapies will be coded using the WHO Drug Reference Listing (WHO DRL) dictionary that employs the WHO Anatomical Therapeutic Chemical (WHO ATC) classification system.

Any concomitant therapies starting prior to or after the start of study treatment will be available at a patient level (listing).

The imputation of a concomitant medication start date will follow the same conventions as for an AE start date (see Section 2.11.1 Adverse events). No imputation will be performed for concomitant medication end dates.

2.9 Analysis of the primary variables

2.9.1 **Primary variables**

The primary endpoints defined to evaluate the safety of LTT462 are incidence and severity of AEs/SAEs, changes in hematology and chemistry laboratory values, changes in vital signs, changes in ECG, and incidence and nature of DLTs (dose escalation only). Tolerability will be evaluated in terms of dose interruptions, dose reductions, and dose intensity.

2.9.2 Statistical model and method of analysis

DLTs (in the dose escalation part) will be analyzed using a BHLRM. The incidence of DLTs will be summarized by system organ class (SOC) and preferred term. The DDS will be used to analyze DLTs.

Statistical analysis of endpoints other than incidence of DLTs will be descriptive, based on the safety analysis set, no hypotheses or models will be considered. Details of analysis are provided in the safety and tolerability sections, respectively. Descriptive statistics will be provided on:

[figure not shown]
- The incidence by patients of AEs, independent of relationship to study drug, and also considering severity
- The incidence by patient of serious AE, independent of relationship to study drug
- Changes from baseline to worst post-baseline hematology and chemistry laboratory values
- Changes from baseline to worst post-baseline values of ECG parameters
- Changes in vital signs from baseline to worst post-baseline values
- Summary of dose intensity, and number and percentage of dose interruptions and reductions

Novartis	Confidential	Page 13
SAP	13-May-2019 (11:03)	CLTT462X2101

2.9.2.1 Dose limiting toxicities (dose escalation)

Statistical model

The dose escalation will be guided by a BHLRM based on the first Cycle DLT data of the study treatment. This model estimates the relationship between dose and the probability of a patient experiencing a DLT following a QD regimen

Dose recommendation

After each cohort of patients, the posterior distributions for the probabilities of DLT rates at different dose levels will be obtained for each stratum. Dose recommendation will be based on posterior summaries including the mean, median, standard deviation, 95%-credible interval, and the probability that the true DLT rate for each dose lies in one of the following categories:

- [0,16%) under-dosing
- [16%,33%) targeted toxicity
- [33%,100%] excessive toxicity

Dose recommendation will also be guided by the EWOC principle, which mandates the dose for the next cohort to have less than 25% chance of excessive toxicity. The final estimate of the MTD/recommended dose for expansion will also satisfy this condition.

Reports

The dose determining set will be used in the following outputs:

- A heatmap (in-text) of the posterior distribution of DLT rates,
- a listing (CSR appendix 16.1.9) of inferential results from the BLRM at the time of the MTD declaration,
- a summary of the DLTs with onset during the first cycle of treatment (dose escalation part only) by primary system organ class, preferred term, and treatment group
- a listing of patients with DLTs reported during the first cycle of treatment.

2.9.2.2 Analysis of other primary Endpoints

Refer to sections 2.11 and 2.12

Novartis	Confidential	Page 15
SAP	13-May-2019 (11:03)	CLTT462X2101

2.10 Analysis of efficacy variable(s)

Tumor response will be determined locally according to RECIST v1.1 (Appendix 1.1 of the study protocol), as per local investigators' assessment. The FAS will be used for all efficacy analyses.

Dose escalation part

For the dose escalation part, the best overall response (BOR) and individual lesions, DOR (if applicable) and the PFS time will be presented for each patient in a listing. PFS, ORR and DCR will be summarized by treatment group.

2.10.1 Confidence intervals for ORR

An exact binomial confidence interval (implemented using the SAS procedure FREQ with the EXACT statement for one-way tables) will be calculated (Clopper CJ, 1934).

2.11 Analysis of safety variables

The assessment of safety is based on the type and frequency of Adverse Events (AEs) as well as on the number of laboratory values that fall outside of pre-determined ranges (Common Toxicity Criteria for Adverse Events (CTCAE version 4.03) grading limits or normal ranges as appropriate). Other safety data include ECOG performance status, electrocardiogram and vital signs.

The Safety set will be used for summaries and listings of safety data with the exception of dose limiting toxicities (DLTs) for which the DDS will be used.

The overall observation period will be divided into three mutually exclusive segments:

- 1. Pre-treatment period: from day of patient's informed consent to the day before first dose of LTT462,
- 2. On-treatment period: from day of first dose of LTT462 to 30 days after last dose of study medication,
- 3. Post-treatment period: starting at Day 31 after last dose of LTT462.

Safety summary tables described in the following sections will include assessments collected during the treatment period, unless otherwise stated.

2.11.1 Adverse events

Data handling

AEs will be coded and graded using the latest version of MedDRA and CTCAE, respectively, available at the time of reporting. If CTCAE grading does not exist for an AE, grades 1, 2, 3, or 4 corresponding to the severity of mild, moderate, severe, and life-threatening, respectively, will be used. CTCAE grade 5 (death) will not be used in this study. Death information will be collected during treatment, safety follow up, and post-treatment follow up.

Progression of malignancy (including fatal outcomes), if documented by use of appropriate method (for example, as per RECIST criteria for solid tumors, should not be reported as a serious adverse event.

Adverse events separate from the progression of malignancy (example, deep vein thrombosis at the time of progression or hemoptysis concurrent with finding of disease progression) will be reported as per usual guidelines used for such events with proper attribution regarding relatedness to the drug.

A patient with multiple CTCAE grades for an AE will be summarized under the maximum grade recorded for the event. A subject with multiple occurrences of an AE is counted only once in the AE category (e.g. SOC, preferred term).

The incidence of a given AE is defined as the ratio of total number of patients experiencing the given AE at least once (defined by its preferred term [PT]) divided by the total number of patients at risk (i.e. part of the safety set). The incidence of AEs will be performed on treatment-emergent events only, i.e., AE that first occurs or worsens during treatment up to 30 days following the last treatment administration. The listing of adverse events will include all events reported during the study conduct.

Reports

The following AE summaries will be produced, including maximum CTC grade 3/4, in addition to the primary analyses:

- AEs regardless of study drug relationship
- AEs suspected to be study drug related
- AEs leading to discontinuation of study drug, regardless of study drug relationship
- AEs which are not SAEs regardless of study drug relationship
- All SAEs regardless of study drug relationship
- On-treatment deaths with cause of death by preferred term
- All deaths, with cause of death by primary system organ class and preferred term

A missing AE start date will be imputed using the following logic matrix described below.

Novartis	Confidential	Page 17
SAP	13-May-2019 (11:03)	CLTT462X2101

Table 2-3	Imputation rules for a partially missing AE start date

	AEM MISSING	AEM < TRTM	AEM = TRTM	AEM > TRTM
AEY MISSING	No imputation	No imputation	No imputation	No imputation
AEY < TRTY	(D)	(C)	(C)	(C)
AEY = TRTY	(B)	(C)	(B)	(A)
AEY > TRTY	(E)	(A)	(A)	(A)

AEM: Month AE started; AEY: Year AE started

TRTM: Month treatment started; TRTY: Year treatment started

Table 2-2 is the legend to the logic matrix shown in Table 2-1 and details the relationship of AE start date to study treatment start date.

 Table 2-4
 Imputation legend and AE/treatment start date relationship

	AE start date relationship	Imputation
(A)	After treatment start or Uncertain	MAX(01MONYYYY, TRTSTD+1)
(B)	Uncertain	TRTSTD+1
(C)	Before treatment start	15MONYYYY
(D)	Before treatment start	01JULYYYY
(E)	After treatment start	01JANYYYY

Before treatment start: Partial date indicates AE start date is prior to treatment start date. After treatment start: Partial date indicates AE start date is after treatment start date.

Uncertain: Partial date insufficient to determine relationship of AE start date to treatment start date.

No imputation will be performed for AE end dates.

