4.1 Description of study design

This study is a Phase I, open-label, dose finding study with a dose escalation part and a dose expansion part in adult and adolescent patients with advanced solid tumors harboring documented MAPK pathway alterations. The study treatment will be taken until the patient experiences unacceptable toxicity, progressive disease and/or has treatment discontinued at the discretion of the Investigator or the patient, or due to withdrawal of consent.

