7.1.4 Treatment period

Treatment period is applicable for both dose escalation and dose expansion parts.

The treatment period will begin on the first day when patient receives LTT462. [REDACTED]
[REDACTED]
[REDACTED]
[REDACTED]

A treatment period cycle is defined as 28 days (4 calendar weeks) for the purposes of scheduling procedures and evaluations. Please refer to [Table 7-1](#) for details of the timing of required assessments and [Section 7.1](#) for visit windows.

Patients will be treated until the patient experiences progression of disease, development of unacceptable toxicity, withdrawal of informed consent, or death, whichever occurs first as described in [Section 7.1.5](#) and [Section 7.1.6](#).

Patients who have disease progression and have evidence of clinical benefit, such as disease shrinkage at other sites or symptomatic improvement, may continue treatment with LTT462. In addition, LTT462 treatment may be temporarily interrupted to permit local therapy for symptomatic metastases after disease progression has been documented. Patients who continue on treatment after disease progression should discontinue study treatment once they are no longer deriving benefit as assessed by the investigator. These decisions can only be taken upon documented agreement with the Novartis Medical monitor and a report of the discussions with Novartis must be recorded in the source documentation and in a comment in the eCRF.

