Summaries will be produced by treatment group for the dose escalation part, by study arm for the expansion part, and overall. Categorical data will be presented as frequencies and percentages. For continuous data, mean, standard deviation, median, minimum, and maximum will be presented.

The primary CSR will include all patients' data reported in the study up to the time when all patients have had the opportunity to complete at least 6 cycles of treatment or discontinued the study. Any additional data reported past this data cutoff date for the primary CSR will be reported in a closeout CSR once all study patients have discontinued the study (refer to [Section 4.3](#)).

The following rules will be followed for reporting results unless stated otherwise:

- a. Dose escalation: cohorts with the same dose level , regimen, [REDACTED] will be pooled into a single treatment group. All tables, figures and analyses will be produced by treatment group.

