2.1 Data analysis general information

Study data will be analyzed by Novartis personnel and/or designated CRO(s) using R

available in the programming environment

PK parameters will be calculated using non-compartmental methods available

Data from participating centers will be combined, so that an adequate number of patients will be available for analysis. No center effect will be assessed. The data will be summarized with respect to demographic and baseline characteristics, efficacy observations and measurements, safety observations and measurements, and all relevant pharmacokinetic (PK) and pharmacodynamics (PD) measurements using descriptive statistics (n, mean, standard

The primary clinical study report (CSR), if final DBL has not occurred, will include all patients' data reported during the dose escalation and dose expansion parts up to the time when all patients have potentially completed at least six cycles of treatment or discontinued the study. The primary CSR will include all outputs planned within the TFL shells document. A final (or closeout) CSR will be produced once all patients have discontinued the study.

Novartis	Confidential	Page 7
SAP	13-May-2019 (11:03)	CLTT462X2101

deviation, median, minimum, and maximum) for quantitative data and contingency tables (frequencies and percentages) for qualitative data.

Both pre and post intra-patient dose escalation data will be listed and summarized together under the one dose level/treatment group.

Cohorts of patients treated during the dose escalation part with the same dose levels, regimen will be pooled into one single *treatment group*.

Below an illustration of the grouping, there will be no difference between safety and efficacy layout of outputs (more details are included in the TFL shells document).

Table 2-1General display of information

		Dose Escalation		
	Treat	Treat	Treat	All
	A	B	C	patients
	N=xx	N=xx	N=xx	N=xx
	n (%)	n (%)	n (%)	n (%)
variable	xx	xx	xx	xx
	(xx.x)	(xx.x)	(xx.x)	(xx.x)
variable	xx	xx	xx	xx
	(xx.x)	(xx.x)	(xx.x)	(xx.x)
variable	xx	xx	xx	xx
	(xx.x)	(xx.x)	(xx.x)	(xx.x)

If during the course of the study different groups of interest are identified, the SAP will be updated accordingly.

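### AE and SAE incidence by dose group is a crude proportion over windows of unequal length, so later-onset AEs are understated in groups that stop treatment early

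*SAP*

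**What the plan says.** - **Endpoint.** SAP 2.9.1: "The primary endpoints defined to evaluate the safety of LTT462 are incidence and severity of" AEs and SAEs, alongside laboratory, vital-sign, ECG and DLT measures. SAP 2.9.2 makes everything except DLTs descriptive.
- **Estimator.** SAP 2.11.1 takes the number of patients with the event at least once, "divided by the total number of patients at risk (i.e. part of the safety set". This is a head count.
- **Window.** SAP 2.11 defines the on-treatment period as "from day of first dose of LTT462 to 30 days after last dose of study medication". SAP 2.11.1 counts an "AE that first occurs or worsens during treatment up to 30 days following the last treatment administration".
- **What closes the window.** Protocol 4.1: "The study treatment will be taken until the patient experiences unacceptable toxicity, progressive disease", or the investigator or patient stops it, or consent is withdrawn.
- **Cut-off.** SAP 2.1 takes data for the primary report "up to the time when all patients have potentially completed at least six cycles of treatment or discontinued the study". Protocol section 10 has the same rule. Protocol 7.1.4 sets the cycle at 28 days.
- **Layout.** SAP 2.1 tabulates by dose and regimen group.

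DLTs have a fixed window: Protocol 6.2.4 limits them to the first 28 days. SAP 2.8.1 summarises duration of exposure, but in separate tables.

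**The concern.** The length of each patient's window depends on how well the treatment is tolerated and how fast the disease progresses. Two dose groups with the same underlying rate of an AE will show different percentages if one group stays on treatment longer. A group with a higher rate can show the same percentage as a group with a lower one.

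This bears on the primary objective, which includes identifying a recommended dose and regimen. Protocol 6.2.3.1 bases that dose on all study data and allows it to lie below the MTD if safety review supports that. The introduction to the SAP says its outputs may also serve for declaring the MTD or the expansion dose. Toxicity that appears after Cycle 1 is what the DLT model cannot show, and that is where the crude percentages are least comparable between groups.

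A smaller point may add to this. Protocol 6.2.3.4 allows intra-patient escalation after four cycles, and SAP 2.1 keeps the data before and after escalation in one dose group. If that is the original group, AEs arising at a higher dose are added to patients who have already been treated for a long time.

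**Working it through.** The documents give no AE rate and no treatment duration by dose, so there is no figure of theirs to reproduce. The window rule, the 28-day cycle and the six-cycle cut-off come from the documents. All hazards and durations below are assumptions.

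**1. Window lengths.** Window = days on treatment + 30.
- One cycle: 28 + 30 = 58 days.
- Two cycles: 56 + 30 = 86 days.
- Six cycles: 168 + 30 = 198 days.

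The ratios are 198/58 = 3.4 and 198/86 = 2.3.

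**2. Same constant hazard in every group.** Set the hazard so that 4 weeks of dosing gives 30%: h = −ln(0.70)/(4 + 30/7) = 0.0430 per week. Incidence with w weeks of dosing is 1 − exp(−h(w + 30/7)).

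| Weeks of dosing | Window (weeks) | Crude incidence |
|---|---|---|
| 4 | 8.3 | 30% |
| 8 | 12.3 | 41% |
| 16 | 20.3 | 58% |
| 24 | 28.3 | 70% |

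From a 20% base at 4 weeks, the values at 8, 16 and 24 weeks are 28%, 42% and 53%. From a 40% base they are 53%, 71% and 83%.

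**3. Hazard ratio hidden by the window.** Equal crude incidence over 58 and 198 days requires a hazard 198/58 = 3.4 times higher in the short-window group. For 86 against 198 days the ratio is 2.3.

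**4. Toxicity, progression and cut-off all ending treatment.** This is a simulation of 400,000 patients per group. Median time to progression is 112 days and the cut-off is at 168 days. Median time to treatment-ending toxicity is 2,000, 200 or 40 days (low, middle, high). A second, unrelated AE has the same hazard in all groups, −ln(0.60)/198 per day, which is 7.85 per 100 patient-months of 30.4375 days.

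| | Low | Middle | High |
|---|---|---|---|
| Mean window (days) | 131.9 | 113.1 | 71.7 |
| Treatment-ending toxicity, crude | 3.6% | 28.9% | 72.3% |
| Other AE, crude | 27.9% | 24.5% | 16.5% |
| Either event, crude | 30.7% | 47.4% | 77.1% |
| Other AE per 100 patient-months | 7.8 | 7.9 | 7.8 |

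When the other AE's hazard is doubled in the high group, its crude incidence there is 29.5% against 27.9% in the low group. The exposure-adjusted rates are 15.6 and 7.8.

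**5. Early onset.** Every treated patient's window runs at least 30 days past the last dose. An AE starting in the first 28 days therefore falls inside it, barring death, withdrawal of consent or loss to follow-up.

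**The case against.** A reader might infer that doses stopped for toxicity will look safer overall, or that the dose-toxicity gradient will be reversed. The documents do not support that. The AE that ends treatment is counted in the incidence and has its own table in SAP 2.11.1, and in step 4 the most toxic group looks clearly worst on treatment-ending toxicity and on either event. Only other AEs, chiefly later ones, are diluted. Toxicity also does not always close the window: Protocol 6.3.1 allows dose reduction, and SAP 2.3 keeps such a patient in the assigned-dose group.

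A reader might also infer that dose escalation itself is biased. It is not. The DLT model uses a fixed 28-day window with a minimum-exposure rule, and Protocol 6.2.3.2 and 6.2.4 already bring Cycle 1 grade 2 or higher toxicity into those decisions.

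The gap between 30% and 70% should not be read as an expected size. It needs a constant hazard and assumed durations, and front-loaded events would shrink it. With cohorts of 1 to 6 patients, one patient moves a cohort's percentage by 17 to 100 points, so chance may outweigh this bias in a single cohort. Exposure, dose intensity, interruptions and reductions are reported, nothing is tested, and the AE listing has no date limit.

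All of this narrows the scope. What remains is that separate exposure summaries cannot correct the percentage for a particular AE. Some SAP text is blacked out and the table shells are not available, so an adjusted table may exist that cannot be seen here.

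**Conclusion.** The concern holds for later-onset AEs and for AEs other than the one that ended treatment. In groups with short treatment, whether through toxicity or progression, their crude incidence is understated relative to groups treated longer. Illustrative sizes, under a constant hazard and assumed durations, are 30% against 41% (4 against 8 weeks of dosing) and 30% against 70% (4 against 24 weeks). In the simulation a true doubling of the rate was almost invisible in the crude percentages. Treatment-ending AEs, early-onset AEs and the DLT model are not materially affected.

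This does not invalidate the planned tables. It is an inexpensive improvement to dose comparisons that can feed the recommended dose.

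**What to change.** Keep the whole-treatment crude AE and SAE tables as the primary description. In SAP 2.11.1 and the table shells, add by dose and regimen group:

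- **(a) Exposure-adjusted incidence:** patients with the event per patient-month at risk. Time is censored at the earliest of first event, last dose + 30 days, or data cut-off. Show patient-months beside the crude percentages, and assign time after intra-patient escalation to the same group as the events.
- **(b) A supplementary table** of AEs with onset in the first 28 days, all grades and grade 3/4.

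Table (b) should stay supplementary. Under the hazard in step 2, incidence over 28 days is 1 − exp(−0.0430 × 4) = 16%, against 70% over the 24-week group's full window. Making it the main comparison would leave out most of the late toxicity.

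The cost is SAP and shell wording, a date filter, a person-time denominator and a few more tables, with no new data collection. The rate is easiest to interpret when the hazard is roughly constant, which is why the crude and 28-day tables should sit beside it.
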